Preliminary (unpublished) evidence from our chemistry lab at the Yale Tobacco Center of Regulatory Science (TCORS) have indicated that it may be possible to reduce acetal formation simply by adding water to e-liquids. This reduces acetal formation by shifting the chemical equilibrium of the formation reaction. Water is physiologically innocuous to inhale via e-cigarette and adding water to e-liquids may be an elegant way to reduce the sensory irritation and cytotoxicity of e-liquids that contain flavor aldehydes. However, adding water also inherently dilutes the flavor and nicotine concentration of the product, which may reduce the appeal overall. This could be a negative outcome if trying to use flavors as a tool to shift combustible cigarette users to potential reduced harm e-cigarettes. However, if irritation is reduced and appeal is not significantly reduced, a regulation requiring a fixed level of water to e-liquids could be a simple and effective tool to reduce potential toxicity in e-liquids with these flavors. *The goal of the proposed study is therefore to determine if the sensory irritation (a marker of potential toxicity) of commercial e-liquids, can be reduced by increasing their water content without adversely affecting flavor appeal in adult e-cigarette users.*

3 Rationale/Significance

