4.1 Hypothesis

We hypothesized that as total water volume is increased in nicotine e-liquids containing flavor aldehydes, sensory irritation experienced by the e-cigarette user will decrease. We do not expect to see this decrease in the control e-liquid (grape e-liquid), which does not contain flavor aldehydes.

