6.2 Assessments

6.2.1 Efficacy

To evaluate the efficacy of manipulating water content on irritation reduction and its potential impact on appeal, we will use the following assessments:

- 1. General Labeled Magnitude Scale (gLMS):** gLMS ratings will be obtain following each 2-puff puff bout. Participants will rate overall intensity, sweetness, coolness, irritation using the gLMS which is a category ratio scale with 7 semantic labels: "no sensation", "barely detectable", "weak", "moderate", "strong", "very strong", and "strongest imaginable". The labels are positioned quasi-logarithmically according to their empirically determined semantic magnitudes²². The gLMS will be displayed on a monitor via a custom LabView® program, and participants will make their ratings using a mouse. Ratings are numerically transformed and then used for statistical analyses. **gLMS irritation will be used to assessed change in irritation (primary outcome), and intensity, sweetness, and coolness will be used to assess change in overall appeal (primary outcome).**
- 2. Labeled Hedonic Scale (LHS)²³:** Liking will be assessed after following each 2-puff puff bout using the LHS scale. The LHS is a bipolar scale with "neutral" in the middle and 5 symmetrical semantic labels: "like/dislike slightly", "like/dislike moderately", "like/dislike very much", "like/dislike extremely", "most liked/disliked imaginable", positioned on the scale according to their semantic magnitude. The LHS yields ratio-level data on the magnitude of liking/disliking of sensation equivalent to that produced by magnitude estimation (ME). This scale will also be displayed on a computer screen as above and numerically transformed. **LHS will be used to assess change in overall appeal (primary outcome).**
- 3. E-cig Effects (Adapted from Drug Effects Questionnaire (DEQ²⁶):** A modified version of the Drug Effects Questionnaire ^{24,27} will be used in which participants will rate

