acute responses to the e-cig on a 0 to 100 mm scale, from “not at all” to “extremely.” Following each 10-puff bout, we will assess E-cig Liking/Wanting (average of “I feel good e-cig effects”, “I want more of that e-cig I received”, “I feel the e-cig strength” and “I like the e-cig effect”). At baseline and following each fixed-dose bout, we will also assess Stimulant effects (average of “I feel energized” and “I feel high”), and Nicotine Withdrawal (average of “I feel sleepy”, “I feel angry”, “I feel irritable”, “I am having difficulty concentrating”, “I feel restless” and “I feel hungry”). **E-cig Effects will be used to assess change in overall appeal (primary outcome).**

4. Multiple Choice Questionnaire to assess e-cig value (Adapted from Multiple Choice Procedure (MCP))^{25,26}: At the end of each 2-puff puff bout, participants will be asked to make discrete hypothetical choices between 10-puffs of the e-cig they had just used or a series of 44 monetary values (\$0.25-\$15.06). The minimum monetary value at which money is chosen over the e-cig puffs is a contingency-based estimate of e-cig value. At the end of each lab session, participants will be given a choice between another 10 e-cig puffs or one of the monetary amounts they picked in the MCPs completed earlier. **MCP will be used to assess change in overall appeal (primary outcome).**

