6.4.2 Sample Size Considerations

Given this is a pilot study, formal power analyses were not conducted. However, based on prior pilot data in which brief lab exposure to e-cigarettes were conducted by our group (HIC 2000025687) determined that 30 participants is sufficient to detect large differences of irritation and appeal by water concentration at two sided alpha level of 0.05.

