6.5 Planned Analyses

6.5.1 Primary Objective Analysis

To examine the primary objective of the study, which is to examine how increasing the concentration of e-liquids with aldehyde flavor chemicals impacts sensory perception of irritation and appeal among current adult e-cigarette users, we will use mixed effects models with water concentration as the within subject factor and each of the measure (e.g. irritation, gLMS and appeal, LHS) as outcomes in separate models. A significant main effect of condition will be considered supportive of our hypothesis. We will construct confidence intervals for least square means and contrasts between least square means to estimate effect sizes and to inform future studies.

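### The success sentence names neither outcome nor direction, so read literally an effect on an appeal score, or a rise in irritation, would support a hypothesis that irritation falls

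*Combined protocol and SAP*

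**What the plan says.** Section 6.5.1 makes water concentration the within-subject factor and takes "each of the measure (e.g. irritation, gLMS and appeal, LHS) as outcomes in separate models". The next sentence is the decision rule: "A significant main effect of condition will be considered supportive of our hypothesis". Section 6.4.1 carries the same rule. Neither section says which model it refers to, which direction is needed, or how many models must be significant.

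The protocol has one hypothesis, in 4.1. As water rises in aldehyde e-liquids, "sensory irritation experienced by the e-cigarette user will decrease". For the control it adds: "We do not expect to see this decrease in the control e-liquid (grape e-liquid"). Appeal is not mentioned there. Appeal enters through the primary objective (4.2), which asks whether it decreases, and through 2.2, where the favorable scenario is "if irritation is reduced and appeal is not significantly reduced".

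The set of primary scores varies by section:

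- The synopsis lists gLMS irritation, LHS and DEQ.
- Section 5.2 lists irritation, DEQ liking, DEQ stimulation, LHS, gLMS sweetness and the Multiple Choice Questionnaire.
- Section 6.2.1 goes furthest. Besides gLMS irritation it says of other gLMS ratings that "intensity, sweetness, and coolness will be used to assess change in overall appeal (primary outcome"), gives LHS and E-cig Effects the same label, and ends with "MCP will be used to assess change in overall appeal (primary outcome").

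The only significance level stated is the "two sided alpha level of 0.05" in 6.4.2. No hierarchy or multiplicity adjustment appears.

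**The concern.** The rule and the hypothesis do not match in three ways.

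- **Outcome.** The rule follows a list of models that includes appeal, while the hypothesis concerns irritation. An effect on sweetness or liking says nothing about whether irritation fell.
- **Direction.** A main effect of a four-level factor is an undirected test. A significant irritation model could reflect irritation rising with water. A significant LHS model could reflect the loss of appeal that 2.2 treats as unwelcome.
- **Number of chances.** With several scores marked primary and each tested at 0.05, the chance of finding some significant effect exceeds 5%. The lists disagree, so the number of chances is not fixed in advance.

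What is at stake is the headline claim. Section 2.2 says that added water inherently dilutes flavor and nicotine, so real effects on intensity, sweetness or liking are plausible whatever happens to irritation. Under the literal rule, such an effect could be reported as support for the irritation hypothesis. Section 3.2.2 says the results could inform legislation.

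**Working it through.** **The plan's own figure.** Section 6.4.2 says 30 participants suffice for large differences. It gives no effect size, standard deviation, correlation or power, so the figure cannot be reproduced. The point does not depend on it.

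**Step 1: count the primary scores.**

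- Synopsis: irritation + LHS + DEQ = 3, or 5 if the DEQ is scored as three subscales.
- Section 5.2: irritation + DEQ liking + DEQ stimulation + LHS + sweetness + Multiple Choice Questionnaire = 6.
- Section 6.2.1: irritation (1) + intensity, sweetness, coolness (3) + LHS (1) + E-cig Effects (Liking/Wanting, Stimulant, Withdrawal: 3) + MCP (1) = 9, or 7 if E-cig Effects is one score.

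**Step 2: chance of at least one false supportive result.** This assumes that any one score counts, that each is tested at 0.05 (the level in 6.4.2), and that water affects none of them. For k independent scores the chance is 1 − 0.95^k:

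- k = 3: 1 − 0.857 = 14%
- k = 5: 1 − 0.774 = 23%
- k = 6: 1 − 0.735 = 26%
- k = 7: 1 − 0.698 = 30%
- k = 9: 1 − 0.630 = 37%

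**Step 3: allow for correlation.** Scores from the same puffs will be correlated, and the documents give no value. I simulated 30 participants, four water levels, one value per participant and level, and a repeated-measures F test on 3 and 87 degrees of freedom, with equal correlation between scores (40,000 runs per cell):

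| Assumed correlation | 3 scores | 6 scores | 9 scores |
|---|---|---|---|
| 0.3 | 14% | 25% | 33% |
| 0.5 | 13% | 22% | 28% |
| 0.7 | 11% | 17% | 21% |
| 0.9 | 9% | 11% | 13% |

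Every cell exceeds 5%. If only the irritation model counts, k = 1 and the rate is 5%.

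**Step 4: a real effect on an appeal score only.** Suppose dilution has a large effect on one appeal score, taken as f = 0.4 over four levels, and none on irritation. With n = 30, m = 4 levels and within-subject correlation ρ = 0, the noncentrality is f²·n·m/(1 − ρ) = 0.16 × 30 × 4 = 19.2. The F test on 3 and 87 degrees of freedom then has power 0.96, and more if ρ is above 0. On the literal rule, support would be declared at least 96% of the time although irritation is unchanged. Both f and ρ are assumptions.

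**The case against.** The strongest reply is that the rule speaks of one hypothesis, that 4.1 is the only one, and that it concerns irritation. Read together, the irritation model is the natural referent, and the percentages above then do not apply. This largely stands as an account of intent: the text says neither any nor all. It does not remove the fault, because the sentence directly follows a list that includes appeal, and nothing limits it. It also leaves direction open, since a rise in irritation would still qualify.

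Four further replies have weight:

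- Nine is the upper count, and the shorter lists give 3 to 6. A reader might infer that the plan sets an explicit any-of-nine rule with a 37% error rate. The documents do not establish that.
- The error rates assume water changes nothing, whereas 2.2 expects dilution. The more realistic risk is therefore the one in step 4, which a family-wise rate does not measure.
- A reader might also infer that a significant appeal model would usually mean appeal was lost. An undirected test does not show that, and nothing ties a change in coolness, stimulation or withdrawal to lower appeal. Testing appeal is itself legitimate, since 4.2 asks about it.
- This is a 30-person pilot without formal power analysis, and it plans confidence intervals to inform later work. That lowers the consequence, and it makes multiplicity adjustment of the appeal scores a matter of preference.

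**Conclusion.** The concern holds as a fault in a stated rule and should be fixed. Followed literally, 6.4.1 and 6.5.1 would let an appeal effect in either direction, or a rise in irritation, count as support for 4.1. The mismatch of outcome and direction rests on the text alone.

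The size of the false-support rate is conditional on any one score being enough and on 0.05 per score. It is 14% to 37% for 3 to 9 independent scores and about 11% to 21% at an assumed correlation of 0.7. It falls to 5% if only the irritation model was meant. The planned intervals and the pilot purpose keep this below a fault that must be corrected before the study can be interpreted at all.

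**What to change.** 1. In 6.4.1 and 6.5.1, restrict the success sentence to the gLMS irritation model at two-sided 0.05, and require the water contrast to show a decrease in irritation in the aldehyde flavors, as 4.1 states. Restricting the outcome alone is not enough, because the undirected test would still accept a rise.
2. State that no appeal model counts as support for 4.1.
3. Name LHS, already the appeal example in 6.5.1, as the key appeal score, reported with its confidence interval. Treat the remaining scores as supportive, also with intervals. Multiplicity adjustment of these is optional.
4. Align the primary outcome lists in the synopsis, 5.2 and 6.2.1.

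These changes do not test the other half of 4.1, the absence of a decrease in grape. That needs a comparison with grape, which a water main effect does not provide.

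The cost is wording in five places (synopsis, 5.2, 6.2.1, 6.4.1, 6.5.1). No assessment is dropped and no participant added. The small downside is that fewer scores keep the label primary, including the DEQ, which the synopsis names beside LHS.

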4.2 Primary Objective

The primary objective of this study is to examine whether (a) sensory irritation and (b) appeal are decreased in e-liquids containing flavor aldehydes (i.e. vanilla, cherry, cinnamon) compared to e-liquids not containing flavor aldehydes (i.e. grape) when the water concentration is increased from the baseline water concentration to the following levels; 5% total water volume, 10% total water volume, 20% total water volume.

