E-liquid Administration/Participant Instructions/Pausing due to AEs: Participants will be administered e-liquid in an observed laboratory setting in which they are instructed to take two directed puffs of each e-liquid at each water concentration. Between 2-puff puff bouts, participants will be required to wait 10-minutes before engaging in next puff bout. Participants are not allowed to leave the site with product. There will no changes in nicotine concentration (only flavor administered) and all participants will sample all flavor/water concentration manipulations. The lab sessions will be conducted by trained research staff who are sensitive to the adolescent and smoking population and trained to monitor any potential adverse effects. Heart rate, blood pressure, and pulse oximetry will be assessed at baseline and every in-person visit for safety. If they experience any side effects or concerns during the study, we ask them to let us know. Participants will be told that they are able to stop the study at any point. If they feel any discomfort or need to stop for any reason, they can let the research team know. In the event of a serious adverse event, the PI ([name]), will consult with Yale Tobacco Center for Regulatory Science (TCORS; the funder of

this pilot) co-Is, [name] [name] and [name], along with center chemosensory expert [name] to determine if blind needs to be broken. Given all study participants are administered all e-liquids, the study will be paused during this period.

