6.1.4 Method of Assignment/Randomization

All participants will receive every flavor/water concentration (4 e-liquids flavors at 4 water concentrations = 16 total manipulations). Participants and research assistants will be blinded to flavors administered. We will use block randomization to determine order flavors are presented in. Water concentration will be presented from hypothesized least irritating to most irritating (20% water, 10% water, 5% water, no alteration).

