completion of baseline assessments, at Lab 1, participants will be familiarized with the sensory and hedonic scales and trained in how to puff the e-cigarette (using non-nicotine and non-flavored e-liquid). Participants will then begin testing procedures for their assigned Flavor 1, which will be administered under double-blinded randomized conditions (see above). For each flavor, participants will take two puffs of the flavor when diluted by four levels of water concentration. Participants will be instructed to take two 3-second puffs with a 30 second inter puff interval. Each two-puff bout will be separated by 10-minutes. These procedures are adapted from our recent work (HIC #2000023077), with the number of puffs is reduced as we are not examining the effects of nicotine and only sensory effects of flavor. Per our current practice we will record timed instructions for each puff bout and participants will be trained to follow these directions. Following each puff exposure participants will complete the General Labeled Magnitude Scale (gLMS) for measures of overall intensity, irritation, coolness and sweetness, the Labeled Hedonic Scale (LHS) for measures of liking, the E-Cig Effects Questionnaire for measures of e-cigarette drug effects, and the Multiple-Choice Questionnaire to assess e-cigarette value. Participants will complete the above procedures for two flavors and four water concentrations for each flavor during each lab session. For each flavor, water concentration order will not be randomized and will be presented from hypothesize least irritating (20% water concentration) to hypothesized least irritation (e-liquid as commercially available with no water dilution) to a) maintain consistency of presentation of water concentration across flavors and b) to avoid potential irritation effects from hypothesized more irritating products to less irritating products. Following at least 24 hours, participants will repeat procedures with the remaining two flavors. Each lab session will last approximately two hours.

Debrief

At the end of Lab 2, participants will be thanked for their participation and ask to evaluate the four flavors they sampled (i.e. guess what flavors they tried, what nicotine concentration they e-liquids were) and will be given information from the CDC on e-cigarette cessation.

Table 1. List of Study Assessments

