6.5.2 Secondary Objectives Analyses

For the secondary aim, which is to examine differences by flavor for outcomes at each water concentration, we will examine at each water concentration, flavor as the within subject factor and each of the measure (e.g. irritation, appeal) as outcomes in separate models. We will construct confidence intervals for least square means and contrasts between least square means to estimate effect sizes and to inform future studies.

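### The primary rule counts any water main effect as support, so it cannot separate the stated hypothesis (a fall in irritation in aldehyde liquids but not in grape) from a water effect shared by all flavors

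*Combined protocol and SAP*

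**What the plan says.** Section 4.1 predicts that irritation falls as water rises in aldehyde liquids, and says of the control: "We do not expect to see this decrease in the control e-liquid (grape e-liquid), which does not contain flavor aldehydes". Section 4.2 words the primary objective as aldehyde liquids "compared to e-liquids not containing flavor aldehydes (i.e. grape"), for both irritation and appeal.

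Section 6.5.1, repeated in 6.4.1, gives the primary model: "we will use mixed effects models with water concentration as the within subject factor". Its support criterion is: "A significant main effect of condition will be considered supportive of our hypothesis". Least-squares-mean contrasts are planned, but none is named between aldehyde liquids and grape.

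The secondary analysis in section 6.5.2 is: "we will examine at each water concentration, flavor as the within subject factor". Section 5.2.2 shows an interest in whether the effect of water varies by aldehyde flavor, but no analysis section carries a water-by-flavor term.

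On exposure, section 6.1.4 fixes the order: "Water concentration will be presented from hypothesized least irritating to most irritating (20% water, 10% water, 5% water, no alteration"). Section 6.3 agrees: "For each flavor, water concentration order will not be randomized". Section 6.1.1, in contrast, speaks of randomized order. The e-liquid administration paragraph (under 6.1.2 and 6.1.3) states: "There will no changes in nicotine concentration (only flavor administered"). Section 2.2 accepts that added water dilutes both flavor and nicotine.

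**The concern.** The hypothesis concerns a difference between two water effects, and the decision rule looks at one. A main effect of water is compatible with the hypothesis, with an equal response in all four flavors, and, since the rule has no direction, even with a rise in irritation.

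This matters because two things besides aldehyde chemistry change with water level in every flavor. Adding water to finished 36 mg/ml liquid lowers nicotine and flavorant. And because the order is fixed, water level is aliased with position: the native liquid always comes three bouts, or six puffs, after the 20% liquid of the same flavor. The grape control is the design's means of offsetting such shared influences, and the primary analysis does not use it that way. A mechanism could therefore be credited to aldehydes or acetals on evidence that does not bear on it.

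**Working it through.** **1. Can any planned analysis test the hypothesis?** Let D be the 20%-minus-native change in aldehyde liquids and g the same change in grape. The hypothesis is that D is a fall and g is not.
- Primary model, all four flavors pooled: it estimates (3D + g)/4, which is 0.75D if g = 0 and D if g = D.
- Primary model, aldehyde liquids only (the wording of 6.5.1 allows this): it estimates D whatever g is.
- Contrasts from a model with water as the only factor compare water levels, not flavor types.
- The secondary models compare flavors within one water level. They test differences in level, not in change.

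None of these estimates D − g.

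**2. The plan's own figure.** Section 6.4.2 says 30 participants suffice for large differences by water concentration at two-sided 0.05. It gives no power, SD or effect size, so it cannot be reproduced. It is plausible for a water effect: a paired t test with n = 30 has 80% power at a standardized difference of 0.53, and 98.9% at 0.8 (assumed here to be large). It does not address the aldehyde-versus-grape difference.

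**3. Size of the dilution.** Nicotine is about 36(1 − T)/(1 − W0), with T the target and W0 the native water. The percentages in section 6.1.3 are by weight, so mg/ml values are approximate. W0 = 1% is the protocol's illustration; no measured value is given.
- T = 5%: 36 × 0.95/0.99 = 34.5, a fall of 4%.
- T = 10%: 36 × 0.90/0.99 = 32.7, a fall of 9%.
- T = 20%: 36 × 0.80/0.99 = 29.1, a fall of 19%.

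For an assumed W0 of 0 to 5%, the fall at T = 20% is 20.0 to 15.8%.

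**4. How often the rule declares support with no aldehyde-specific effect (g = D).** Assume a single-flavor change is a shared participant part (variance r) plus an independent flavor part (variance 1), so its SD is √(1 + r). Variances per participant are r + 1/4 (pooled), r + 1/3 (aldehyde only) and 1/3 + 1 = 4/3 (contrast). With D in units of the single-flavor SD, the standardized effect is D√(1 + r)/√variance. For pooled, r = 0, D = 0.2, this is 0.2/0.5 = 0.40, giving 56% rejection (paired t, n = 30, two-sided 0.05).

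| Shared change D (SD) | 0.2 | 0.3 | 0.4 |
|---|---|---|---|
| Pooled, r = 0 | 56% | 89% | 99% |
| Aldehyde only, r = 0 | 45% | 79% | 96% |
| Pooled, r = 1/3 | 36% | 67% | 89% |
| Aldehyde only, r = 1/3 | 32% | 61% | 85% |
| Aldehyde-minus-grape contrast | 5% | 5% | 5% |

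A simulation of all four water levels with F tests agrees. For a shared effect of 0.3, 0.5 or 0.8 SD of a single rating, the pooled rule declared support in about 50, 94 and 100% of trials and the aldehyde-only rule in about 39, 85 and 99.8%. The interaction test stayed near 5%.

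**5. Precision of the contrast.** The ratio of its standard error to that of the aldehyde-only effect is √((4/3)/(r + 1/3)): 2.0 at r = 0 and 1.41 at r = 1/3. The detectable effect at 80% power is 0.529 × √variance/√(1 + r):
- r = 0: 0.61 SD for the contrast, 0.31 SD for the aldehyde-only effect.
- r = 1/3: 0.53 SD and 0.37 SD.

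**The case against.** This is a pilot. Its contrasts and intervals are meant to inform later work, so a supportive result is not a confirmatory claim. The plan discusses dilution openly (sections 2.2, 3.1 and 3.2.2). The order is justified on chemosensory grounds, and bouts are ten minutes apart. The contrast is also weak at this size: in the same simulation, a true aldehyde-only effect of 0.5 or 0.8 SD of a single rating was detected by the interaction test in only about 27 or 64% of trials. All of this stands. It argues for reporting estimates with intervals, not for a criterion that passes whether or not grape responds.

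The reading that section 6.5.1 means aldehyde liquids only also has force. It lowers the illustrative rates but leaves the defect, because grape is then not compared at all.

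Some stronger readings go beyond the documents:
- A reader might infer that dilution or order would explain any water effect found. The documents give neither effect's size on irritation, and order could act in either direction.
- A reader might infer that the criterion is easier to meet when the hypothesis is false (1.0D against 0.75D). That holds only if all four flavors are pooled, which the plan does not say.
- A reader might conclude that the contrast alone should decide. It can look favorable when aldehyde irritation is flat and grape rises with water, which section 4.1 does not predict.

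**Conclusion.** The mismatch between hypothesis and decision rule is established from the text and needs no assumption: nothing planned estimates the aldehyde-minus-grape difference in the water effect. How often it would mislead depends on an unknown shared effect. The rates above rest on assumed shared changes of 0.2 to 0.4 SD, equal flavor-specific variances, a shared variance of zero or one third of the flavor-specific variance, and a single 20%-versus-native comparison.

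The water effect itself remains relevant to a regulation on water content. What the main effect cannot do is attribute that effect to aldehydes. The plan should be changed; this is not a reason to doubt the data collection.

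**What to change.** 1. **Sections 6.4.1 and 6.5.1.** Add flavor type (aldehyde, grape) and flavor type by water. For gLMS irritation, count the hypothesis as supported only if irritation falls with water within the aldehyde liquids (20% versus native as the headline) and the aldehyde-minus-grape difference favors a larger fall in aldehyde liquids. Report both, and the grape change, with 95% intervals.
2. **Appeal.** Report the water effect within aldehyde liquids as well as the contrast with grape. The contrast cancels any dilution loss common to all flavors, and that loss is what sections 2.2, 3.1 and 3.2.2 worry about.
3. **Exposure wording.** Correct the nicotine sentence in the e-liquid administration paragraph and clarify section 5.1: liquids are supplied at 36 mg/ml, and adding water lowers nicotine and flavorant. Reconcile the randomized order in 6.1.1 with the fixed order in 6.1.4 and 6.3.
4. **Limits to state.** There is one control flavor. The contrast removes dilution and order effects only if they act similarly in every flavor, which cannot be taken for granted since section 2.2 notes that some flavors may soften nicotine harshness. It does not separate less acetal from less aldehyde.

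The cost is one flavor-type factor with its interaction, and some wording. All 16 flavor-by-water cells are already collected. Given the precision shown above, a non-significant contrast would not rule out an aldehyde-specific effect, and the plan should say so.
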